3.5.4 Stage 4 – functional mobility assessment

Functional mobility will be evaluated by the timed up and go protocol. A seat with a back and without lateral support, a cone and a stopwatch will be used.

In this protocol the subject will rise from a chair with the backrest resting on the backrest, will walk three meters in a straight line, make a 180° turn, return to the chair and sit propping the backrest on the chair. This course will be timed in seconds and the performance of the subject will be graded according to the time spent. The protocol allows you to check the total time spent on the task. The subject will perform 3 attempts. The average number of attempts will be.

3.5.5 Stage 5 – postural control

[figure not shown]
The NeuroCom SMART EquiTest CRS balancing platform will be used, with a sampling rate of 100 Hz. The equipment will be calibrated according to the manufacturer's standards. The collections will be made with three dynamic protocols pre-established by the system: Sensory Organization Test (SOT), which verifies the sensory motor control; Motor Control Test (MCT), which verifies the automatic motor control; And Adaptation Test (ADT), which verifies adaptive motor control.

All protocols will be performed in the bipodal position, where the individual will position their feet together, parallel, hands along the body and face facing forward. The tests performed will evaluate the posture control of the participant in static posture with open and closed eyes, without and with movement of the support surface and / or visual environment. The order of the three protocols (SOT, MCT and ADP) will be chosen by lot.

During collection the individual should stand at the base of the platform looking forward. He will wear harness (available in small, medium and large size) connected to safety cables throughout the test. During the test only the presence of the evaluator and one other member of the collection team will be allowed to assist the assessor in case of loss of balance. Both should be close to the individual, but should not interfere with the test.

You will be prompted to look at the screen in front of you and center the puppet (corresponding to the alignment of the participant). Before starting the tests the individual will be informed that the platform and the environment can move during the evaluation, but will not be informed about when this will occur. Afterwards, the researcher will start collecting the data, guiding the participant to keep the doll as centralized as possible without flexing the knees or changing the position of the feet. In cases where the participant uses these or other artifacts to maintain postural control (eg, hold in the environment), the test will be considered a "failure" and the test will continue for the next test.

Figura 1 – Data collection procedure diagram

The data collected in the preoperative period will be used as a comparative baseline to determine changes in gait parameters (spatio-temporal, kinetic, electromyographic), postural control and functionality associated with the presence or absence of information in the preoperative.

Self-perceived functionality, fear of movement and TUG time will be exported to spreadsheet in EXCEL software for further statistical analysis.

The gait analysis data will be analyzed in the Vicon-Nexus software, version 2.1.1, through a processing routine that will include filtering and application of the algorithms. In this analysis, frontal (adduction / abduction of the knee) and sagittal (knee flexion / extension) planes will be considered. In addition, the following space-time parameters will be recorded during the run: (1) step length in centimeters; (2) stride length in centimeters; (3) symmetry of the foot; (4) step and step time in seconds; (5) single and double support time in seconds and (6) the knee adductor moment in response to the load.

The coefficient of variation (CV = standard deviation of pitch duration / average pitch duration x 100%) will be calculated to indicate the individual variability in pitch duration.

The raw electromyographic signals will be processed to obtain the linear envelope following the steps of full wave rectification, filter smoothing with 4th order Butterworth and cutoff frequency of 5Hz. The amplitudes of the linear envelopes will be normalized by the maximum voluntary contraction in each muscle (YANG e WINTER, 1984).

The total time to perform the functional mobility task (TUG) will be set in excel for further analysis.

In the evaluation of postural control, the velocity of oscillation of the center of gravity (in degrees per second) in the six conditions, bipodal support, unipodal support and tandem, both on stable and unstable surfaces will be evaluated. The center of gravity velocity data will be processed in a Matlab routine, where the displacement data (cm) and velocity (ms) of the pressure center (COP) will be extracted in the anteroposterior and mediolateral directions.

APPENDIX A - Guidance for Patients with Total Knee Arthroplasty

The knee is a joint composed of three bones: femur, tibia and patella. Between the femur and the tibia there is a kind of cushion, the cartilage. In a healthy knee, these structures also distribute body weight and allow the movements needed to walk.

Aging can result in wear and tear on this joint, it is osteoarthritis. When the knee becomes very sore and does not move more, it is necessary to change the joint to relieve pain and return the movements to perform daily activities (sitting, walking, climbing and descending stairs). This exchange is done by surgery, called ARTHROPLASTY.

In knee arthroplasty, the bones (tibia and femur) are replaced with very resistant metal. The patella is replaced by a kind of sturdy plastic.

This surgery is performed by a specialized and well trained team and requires special care in the postoperative period. Adequate observation and care also prolong the use of the prosthesis as much as possible. Thus, this guide will present some clarifications in order to enable a faster and better recovery for you as well as better use of surgery.

BEFORE SURGERY

If you have crutches or walkers, do not forget to take them. Will be useful after surgery.

Also remember to take your preoperative exams, including x-rays. The surgery time varies with each case and will be informed by the doctor, but may suffer increases for various reasons without the need for concern of family members.

DURING THE SURGERY

The best anesthesia for you will be chosen by your anesthesiologist.

The surgery cut is done in front of the knee, after removing the damaged bone part and placing the prosthesis. At the end of surgery may be placed drain and dressing that remain for 48 hours.

AFTER SURGERY

Once the anesthetic effect has passed, you will go to the hospital bed and the pain will be controlled with medication.

The physiotherapy team will guide you on how to move in bed and when to start walking.

On the day of discharge we hope that you can already sit, walk with the help of crutches or walker and leave the hospital sitting in the passenger seat with the stretched operated leg.

POSTOPERATIVE GUIDANCE

In the postoperative the objective is to improve the strength, to minimize swelling and to obtain total movement of the operated leg.

DOUBLE AND STRETCH the leg throughout the day. Please follow correctly the recommendations and exercises passed by the team (doctors, nurses and physiotherapists).

- In the first 12 hours after surgery you CAN NOT support the operated limb on the floor, so when sitting on the bed they should be loose.
- You may have PAIN after surgery, even so let the team know.
- BLEEDING and HEMATOMA may occur after surgery, but do not worry, they slowly disappear.
- AVOID lying on the operated legNÃO COLOQUE TRAVESSEIRO embaixo do joelho operado. Tente deixa-lo esticado quando estiver deitado.
- When standing, divide the weight of the operated leg with the crutches and the other leg.
- PLACE ICE on the knee with the leg elevated. Do this at least 3 TIMES a day.
- REMOVE THE CARPETS from the house. LOOK WHERE IT PISA! USE shoes with non-slip sole.
- You CAN HAVE SLEEP AND Stiffness in the knee, especially when folding your knee a lot, for example when sitting and getting up from a low chair or car seat.
- ATTENTION IN THE BATH in the first few days. TAKE INTO THE SEATING POSITION for added safety.
- In the first month, AVOID POSITION SITTING FOR MORE THAN 45 MINUTES. Alternate sitting with walking.

- When sitting, it is important to bend the knee and remember not to leave the limb hard to walk. This will make it easier to move and give you more comfort.
- Kneeling is not harmful but may cause noise due to the material of the prosthesis.
- To UP STAIRS use FIRST NON-OPERATED MEMBER after limb operated and lastly the crutch.
- To lower LADDERS, place FIRST BALL, then MEMBER OPERATED and last member not last operated.
- SPORTS ACTIVITIES only after TOTAL KNEE RECOVERY.
- The intercourse is safe between 4 and 6 weeks, but its beginning depends on care as well as other daily activities.
- To drive you should no longer be taking medication for pain and need to have the release of your doctor.
- Over the weeks the possible distance of walking gradually increases as well as the improvement of the other symptoms. The total benefits of joint replacement usually occur between 6 and 8 months postoperatively.

APPENDIX C - Personal data and follow-up of participants

MASTER IN PHYSIOTHERAPY Preoperative guidance and repercussion in gait after

knee arthroplasty

Name:		Sex: ()F () M
Date of birth / age:		Telefone: ()
Address:		
Date of surgery:	Weight:	Height:
Antonion annonica in the	n anotad an aantralataral lan	

Anterior surgeries in the operated or contralateral knee:

Physiotherapeutic Treatment

PREOPERATIVE - Allocation () GI () GC

Do you do physiotherapy for your knee pain? If yes, how many times in the week?

What treatment time (weeks, months, years)?

Check the type of procedures you perform in the sessions:

() warmth () cold () TENS () US () stretches () strengthening exercises () balancing exercises () Others, which ones?

6 WEEKS AFTER SURGERY - Booklet reading () Yes () No () GC

Are you doing physiotherapy? If yes, how many times in the week? How long after the surgery did you start the sessions? If completed, how many sessions and for how long? Check the type of procedures you perform in the sessions: () warmth () cold () TENS () US () stretches () strengthening exercises () balancing exercises () Others, which ones?

6 MONTHS AFTER SURGERY - Booklet reading () Yes () No ()GC

\mathbf{U}
Are you doing physiotherapy? If yes, how many times in the week?
How long after the surgery did you start the sessions?
If completed, how many sessions and for how long?
Check the type of procedures you perform in the sessions:
() warmth () cold () TENS () US () stretches () strengthening exercises () balancing
exercises () Others, which ones?

ATTACHMENTS

ATTACHMENT A – WOMAC (Western Ontario and McMaster Universities Osteoarthritis

Index)

WOMAC INDEX SECTION A

INSTRUCTIONS:

Answer each question with an "X" in the appropriate box, based on fatigue or the amount of pain you experienced in your muscles. For each situation, enter the amount of pain experienced during the last 48 hours.

QUESTION:

How much pain do you have?

	Nome	Mild	Moderate	Severe	Extreme
1. Walking on a flat surface.					
2. Going up or down stairs.					
3. At night while in bed.					
4. Sitting or lying.					
5. Standing upright.					
			SECTI	ON B	

INSTRUCTIONS:

Answer each question with an "X" in the appropriate box, based on the amount of muscle pain you experienced during the last 48 hours.

1. How severe is your pain after first awakening?

None	Mild	Moderate	Severe	Extreme

2. How severe is your pain after sitting, lying or resting later in the day?

None	Mild	Moderate	Severe	Extreme
i	لسا			

۰.

SECTION C

INSTRUCTIONS:

The following questions concern your physical function. By this we mean your ability to move around and to look after yourself. For each of the following activities, please answer each question with an "X" in the appropriate box to indicate the degree of difficulty you have experienced during the last 48 hours due to pain or fatigue.

QUESTION:

What degree of difficulty did you have with ...

	None	Mild	Mederate	Severe	Extreme
1. Descending stairs.					
2. Ascending stairs.					
3. Rising from sitting.	Ц			Ц	Ц
4. Standing	Ц	Ц	Ц	Ц	Ц
5. Bending to floor.			Ц		
6. Walking on flat surface.	Ц		Ц	Ц	
7. Getting in/out of car.			Ц		
8. Going shopping.					님
9. Putting on sock/stockings					
10. Rising from bed.					H
11. Taking off sock/stocking					
12. Lying in bed.	H		H	H	
13. Getting in/out of bath.	H		H		
14. Sitting.	H	H	H	H	H
15. Getting on/off toilet.	H	H	H	님	H
16. Heavy domestic duties.	H	H		H	H
17. Light domestic duties.		المسل		للسبا	لـــــا

.

.

.

ATTACHMENT B - TAMPA SCALE OF KINESIOPHOBIA

Here are some things other patients told us about their pain. For each statement, please, provide a score from 1 to 4 in case you agree or disagree with the statement. First, you must think if you agree or disagree and then say you agree/disagree entirely or partially.

		Entirely disagree	Partially disagree	Partially agree	Entirely agree
1.	I'm afraid of getting hurt if I exercise.	1	2	3	4
2.	If I tried to overcome this fear, my pain would increase.	1	2	3	4
3.	My body is telling me there is something very wrong happening with me.	1	2	3	4
4.	My pain would probably be relieved if I made some exercises.	1	2	3	4
5.	People are not taking my medical condition seriously.	1	2	3	4
6.	The injury put my body at risk for the rest of my life.	1	2	3	4
7.	Pain always means that my body is hurt.	1	2	3	4
8.	Just because something worsens my pain, it doesn't mean it is dangerous.	1	2	3	4
9.	I'm afraid of getting hurt by accident.	1	2	3	4
10.	The safest attitude I can take in order to prevent my pain from getting worse is just to be careful to not to make any unnecessary movement.	1	2	3	4
11.	I wouldn't fell so much pain if something really dangerous was not happening with my body.	1	2	3	4
12.	Although I feel pain, I would be better if I was physically active.	1	2	3	4
13.	Pain warns me when to stop exercising in order to not getting hurt.	1	2	3	4
14.	It is not really safe for a person with problems similar to mine to be physically active.	1	2	3	4
15	I cannot do all the things normal people do, because I easily get hurt.	1	2	3	4
16.	Although something causes me a lot of pain, I don't think it is really dangerous.	1	2	3	4
17.	Nobody should make exercises when in pain.	1	2	3	4

Table 1 - Tampa Scale for Kinesiophobia - Brazil.

## STATISTICAL ANALYSIS PLAN

Descriptive statistics (mean, standard deviation) will be used to describe the participants involved and results of kinesiophobia cover scale, WOMAC scale, gait analysis and TUG. The spatiotemporal and kinetic parameters, electromyographic activation, TUG and postural control will be analyzed by analysis of variance 3x2 considering time factor (pre, post 6 weeks, post 6 months) and groups (with and without informative leaflet), respectively. If the sphericity hypothesis is rejected, the Huynh-Fedt correction will be applied. Effect sizes will be computed by means of partial square eta values. The SPSS 20.0 package will be used for all analyzes. The p value used will be 0.05.

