SANTA CATARINA STATE UNIVERSITY - UDESC CENTER FOR HEALTH AND SPORTS SCIENCES – CEFID GRADUATE PROGRAM IN PHYSICAL THERAPY

[name]

EFFECT OF PREOPERATIVE PATIENT EDUCATION PROGRAM ON FUNCTIONAL OUTCOMES AFTER TOTAL KNEE ARTHROPLASTY

STUDY PROTOCOL

FLORIANÓPOLIS 2017

ABSTRACT

The knee is one of the joints most affected by osteoarthritis (OA), causing individuals to present joint stiffness, muscle weakness and proprioceptive deficit limiting the performance of daily activities. Total knee arthroplasty (TKA) presents good results in reducing the pain and stiffness of individuals in the final phase of OA. However, changes in gait and strength may persist postoperatively. Preoperative guidance for TKA were efficient in reducing pain and functional deficits and improving quality of life, however the functionality was measured by scales. Thus, this study aims to evaluate the effect of preoperative guidance on three-dimensional gait analysis, functional mobility, postural control and kinesiophobia level in subjects with TKA. Will be recruited patients of both sexes undergo unilaterally TKA in the city of Florianópolis and referred by an orthopedist to the Physiotherapy Clinic of UDESC. These will be divided into two groups: one that will receive verbal guidance and a leaflet with information related to their physical condition as well as signs and symptoms in the postoperative period and a group that will receive only verbal guidance. Both groups will be evaluated by a blind evaluator in the preoperative and postoperative periods (6 weeks and 6 months). The evaluations will be divided into five stages. Anthropometric measurements of the individual will be made and then the WOMAC functionality questionnaire and the Tampa Scale of Kinesiophobia will be applied. Then the individual will walk by 5 meters for three-dimensional gait analysis through the Vicon System, AMTI Force Platforms and Noraxon electromyograph. A functional mobility assessment will also be performed by Timed Up And Go. Finally, evaluation of the postural control with Neurocom Equilibrium Platform will be performed. Statistical data will be analyzed by analysis of variance 3x2 considering time factor (pre, post 6 weeks and post 6 months) and groups (with and without information leaflet). The p-value used will be 0.05.

Palavras-chave: osteoarthrosis, total knee arthroplasty, physiotherapy, gait analysis, guidance

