Investigations of the kinematics in the TKA showed lower flexion in the initial contact phase and less flexion in the oscillation phase. These individuals also had greater varus in response to the load when compared in asymptomatic individuals (VASCONCELOS et al, 2013). Research associating three-dimensional gait assessment with electromyography (EMG) found patterns that differed from normal, but no preoperative data were collected from individuals in order to quantify the changes that occurred (VILLARDI et al, 2005; LEE et al, 2015).

He knows that the variability of step time depends on the sum of factors physical function, ability to balance and mental state, such as the confidence of the individual in his ability to perform the activity (HYIAMA et al, 2015). There is evidence that persistence of pain can not be based solely on clinical findings, making a purely clinical intervention inefficient (SIQUEIRA et al, 2007). Pain education can alter beliefs about pain, such as the fact that it is related to tissue damage and disability (LOUW et al, 2013), Showing reduction of pain, functional deficits and improvement of the quality of life in patients who received guidance for the postoperative period (MONTICONE et al, 2013).

A review study has shown that preoperative guidance themselves can not modify the patient's physical condition but improve the ability to cope with pain and feel prepared for surgery by reducing anxiety and increasing postoperative comfort (AYDIN et al, 2015). Fear of movement pain characterizes kinesiophobia, where the individual ceases to perform activities inducing a vicious cycle, which results in decreased joint mobility, muscular strength and proprioception, thus increasing the pain experience (MONTICONE et al, 2013).

Although there were studies on the effect of preoperative guidance on patients with TKA, mobility was assessed only through functional questionnaires, with no objective information on the behavior of the spatial-temporal and kinetic parameters of gait, postural control and functionality. Thus, this study aims to evaluate the effect of preoperative guidances on functional gait recovery and kinesiophobia level in subjects post TKA.

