1.2 OBJECTIVE

The study was designed to evaluate the effect of preoperative patient education program on functional outcomes after total knee arthroplasty.

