1.3 HYPOTHESES OF RESEARCH

- H0: There is no difference on functional outcomes on functional otucomes after TKA in patients that received preoperative information and those who did not.
- H1: There is difference on functional outcomes on functional otucomes after TKA in patients that received preoperative information and those who did not

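### The SAP leaves the Tampa kinesiophobia score out of its group-by-time ANOVA although the protocol's aim sentences name it; WOMAC is left out too, on weaker grounds

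*SAP*

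**What the plan says.** The SAP has two lists of measures. The first, for means and standard deviations, covers the participants and the "results of kinesiophobia cover scale, WOMAC scale, gait analysis and TUG". The second is inferential: "The spatiotemporal and kinetic parameters, electromyographic activation, TUG and postural control will be analyzed by analysis of variance 3x2", with time (three visits) and group as factors, a sphericity correction if needed, partial eta squared as effect size, and a 0.05 level. No other test is named.

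The protocol describes what the trial is for in several places:

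- **Abstract, aim:** the effect of guidance on gait, "functional mobility, postural control and kinesiophobia level in subjects with TKA".
- **Section 1.1, closing aim:** "this study aims to evaluate the effect of preoperative guidances on functional gait recovery and kinesiophobia level in subjects post TKA".
- **Abstract, analysis:** "Statistical data will be analyzed by analysis of variance 3x2 considering time factor" and group, with no list of outcomes and none excluded.
- **Section 1.2:** "The study was designed to evaluate the effect of preoperative patient education program on functional outcomes after total knee arthroplasty". Kinesiophobia is not named.
- **Section 1.3, null hypothesis:** "There is no difference on functional outcomes on functional otucomes after TKA". Kinesiophobia is not named here either.
- **End of section 3.5.5:** baseline data serve to determine changes in gait parameters, "postural control and functionality associated with the presence or absence of information in the preoperative" period.

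Section 3.5.2 applies both the Tampa scale and WOMAC at all three visits. The data-handling text after 3.5.5 exports the WOMAC, Tampa and TUG results together for later statistical work. Section 3.8 looks forward to confirming a benefit on kinesiophobia and functionality. The blinding text in section 3.2.1 mentions secondary outcomes, but neither document lists them.

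**The concern.** A randomised trial that sets out to evaluate an effect on kinesiophobia needs a comparison between arms on a kinesiophobia measure. The Tampa scale is the only such measure in the protocol. A set of means and standard deviations by visit does not supply an effect estimate, an interval or a test.

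The SAP is the more specific document. An analyst who follows it will test TUG, gait, EMG and postural control and will only describe Tampa and WOMAC. An analyst who follows the abstract will test everything. If this is not settled beforehand, the decision to test these scales could be taken after the results are visible. So could the choice of WOMAC score, since section 3.3.6 speaks of a final score and section 3.4.6 of values for each domain.

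**Working it through.** The plan gives no figure on this point to reproduce. Its one calculation, the sample size, concerns TUG and does not enter here. The check is a comparison of lists, followed by a count of what the fix would add.

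**Step 1: is the scale in the SAP's descriptive sentence the Tampa scale?** Yes. Section 3.4.7, headed Tampa Scale of Kinesiophobia, and section 3.5.2 use the same translated name.

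**Step 2: place each measure.**

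| Measure | SAP descriptive list | SAP 3x2 ANOVA list | Named in the aim sentences (abstract or 1.1) |
|---|---|---|---|
| TUG (functional mobility) | yes | yes | yes |
| Gait | yes | yes | yes |
| EMG | not named | yes | not named separately |
| Postural control | not named | yes | yes |
| Tampa (kinesiophobia) | yes | **no** | **yes, in both** |
| WOMAC | yes | **no** | no |

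Tampa is the only measure that the aim sentences name and the ANOVA list lacks. Its three visits match the ANOVA's time factor, so nothing in the data collection prevents the analysis.

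**Step 3: grade the evidence for each scale.** For Tampa, two aim sentences state an effect to be evaluated. For WOMAC the support is indirect: the phrase functional outcomes in 1.2 and 1.3, the word functionality at the end of 3.5.5 and in 3.8, and the joint export for later analysis. Section 3.3.6 labels WOMAC as self-reported functionality, which makes the link reasonable but does not settle it.

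**Step 4: count the tests that the fix adds** (one group-by-time test per score).

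- Tampa only: 1
- Tampa and the WOMAC final score: 1 + 1 = 2
- Tampa and three WOMAC domains: 1 + 3 = 4

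If there is no true effect and the tests are independent, the chance of at least one p < 0.05 is 1 − 0.95^k:

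- k = 1: 5%
- k = 2: 1 − 0.9025 = 9.75%
- k = 4: 1 − 0.8145 = 18.5%

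If between-arm differences are also reported at 6 weeks and 6 months, that is 2 contrasts per score: 2, 4 or 8. For 8 contrasts alone, 1 − 0.95^8 = 33.7%. Domains of one questionnaire and repeat visits are likely to be positively correlated, which would make the true figures lower. These percentages describe the cost of the fix, not the size of the omission.

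**Step 5: precision at 20 per arm.** For an unadjusted difference at one visit with no dropout, the 95% half-width is about 1.96 × √(2/20) = 0.62 standard deviations. With 10% dropout (18 per arm) it is 1.96 × √(2/18) = 0.65. The documents give no Tampa or WOMAC standard deviation, so this cannot be put in points.

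**The case against.** The strongest reply is that a between-arm analysis already exists in the documents. The abstract applies the 3x2 ANOVA to the data in general, with visits, groups and the 0.05 level all set. The SAP's descriptive list does not mark its entries as descriptive only, since TUG and gait are on it and are also tested. The SAP nowhere says that Tampa or WOMAC will not be compared. This stands to the extent that the defect is a conflict between a general sentence and an itemised one. It does not remove the conflict, because the itemised text is in the SAP and omits an outcome that the aims name.

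A second reply concerns WOMAC, and most of it stands. WOMAC is in neither aim sentence. Section 1.1 criticises the subjectivity of questionnaires and presents objective measurement as the gap to fill, so describing WOMAC without testing it may be deliberate. The word functionality at the end of 3.5.5 could mean performance, and the export for later analysis is satisfied by descriptive statistics.

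A reader might go further and infer that the investigators decided against comparing kinesiophobia, or that a formal hypothesis will go untested. The documents support neither. The abstract's sentence is compatible with a planned comparison. Sections 1.2 and 1.3 do not name kinesiophobia, and section 3.8 states an expectation, not an analysis commitment.

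**Conclusion.** The concern holds for kinesiophobia. Two aim sentences promise an evaluation of effect, the scale is collected at every visit, and the SAP as written provides no between-arm estimate or test. This rests on reading the SAP's ANOVA sentence as a complete list. If the abstract governs instead, the analysis is covered, but the two documents still disagree and should be reconciled.

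For WOMAC the point is a request for clarification: the omission is the same, but the commitment to compare is only suggested. A reader might treat the two scales as equally promised; the aim sentences do not support that.

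The reach is limited to non-primary outcomes. TUG is on the ANOVA list, and neither its analysis, the planned 40 patients nor the visit schedule changes. The point should be fixed because it is cheap and determines whether the trial can answer one of its stated aims.

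**What to change.** In the SAP, before analysis begins:

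1. Add the Tampa score to the 3x2 group-by-time ANOVA, with the same model, sphericity correction and effect size as TUG. Label it secondary and not adjusted for multiplicity.
2. For WOMAC, choose one of two courses. Either add it on the same terms and state in advance whether the final score (section 3.3.6) or the domain scores (section 3.4.6) are analysed, or state that it is descriptive only.
3. Add a matching line in the protocol so that the abstract's ANOVA sentence, the data-handling text and the SAP agree, and name these scales as secondary outcomes where that applies.

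This takes one or two SAP sentences and one protocol line, and no new data. The price is 1 to 4 more secondary tests with limited precision. Between-arm differences with 95% confidence intervals at 6 weeks and 6 months would be informative but optional. They add 2 contrasts per score, up to 8, and the SAP does not currently specify them even for TUG.
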